5 ANALYSIS POPULATIONS

All subjects meeting inclusion/exclusion criteria will be considered enrolled subjects. Those not meeting all inclusion/exclusion criteria will be considered screen failures. Randomized subjects will include all subjects randomized to a treatment arm. Summaries of all subjects (such as those for disposition) will include both enrolled subjects and screen failures.

5.1 Intent-to-Treat (ITT) Population

The ITT population will include all subjects who receive a randomized study procedure (either EPi-Sense-AF or catheter ablation). This population will be used as the primary analysis population for efficacy analyses. Subjects will be analyzed according to randomized treatment.

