### 9.3.1 Intention To Treat (ITT) Population

The ITT population will include all study subjects who receive a randomized procedure. This population will be used for all efficacy analyses. Subjects randomized but with no post-treatment assessments will be imputed (refer to Section 9.4).

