### 9.3.2 Modified Intention To treat (mITT) Population

The mITT population will include all study subjects who receive a randomized procedure and have at least one post-treatment follow-up visit. This population will be used for all efficacy analyses.

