### 9.3.3 Per Protocol (PP) Population

The PP population will include all study subjects who receive their randomized procedure who have at least four of the five first year visits and who have no major protocol violations or deviations. This population will be used for the primary efficacy analysis.

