5.2 Modified Intent-to-Treat (mITT) Population

The mITT population will include all subjects who receive a randomized study procedure (either EPi-Sense-AF or catheter ablation) and have at least one post-procedure follow-up visit after the 3 month blanking period (as described in Section 7.4.2) with non-missing efficacy results. This follow-up visit is defined as a visit with echocardiogram, rhythm disturbance evaluation, or Holter monitor results, after the end of the blanking period. This population will be used to support efficacy analyses. Subjects will be analyzed according to randomized treatment.

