5.3 Per Protocol (PP) Population

The PP population will include all subjects who receive a randomized study procedure (either EPi-Sense-AF or catheter ablation) who have at least four of the five first year visits (that is, at least 4 of the 7 day, 1 month, 3 months, 6 months, and 12 months visits are completed) and who have no major protocol violations or deviations. This population will be used for sensitivity analysis of the primary efficacy analysis.

A blinded list of all protocol deviations will be provided to the Medical Monitor to be categorized (major or minor) prior to study unblinding and database lock, as described in Section 8.3.

Subjects will be analyzed according to randomized treatment.

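### The set called ITT holds only treated subjects, so no planned efficacy analysis covers all randomized subjects, although one post-randomization exclusion applies to the convergent arm alone

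*SAP*

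**What the plan says.** Protocol 9.3.1 sets the rule: "The ITT population will include all study subjects who receive a randomized procedure". SAP 5.1 repeats it and makes this the primary efficacy set: "The ITT population will include all subjects who receive a randomized study procedure (either EPi-Sense-AF or catheter ablation".

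The other efficacy sets start from the same condition:

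- mITT: "The mITT population will include all study subjects who receive a randomized procedure and have at least one post-treatment follow-up visit" (Protocol 9.3.2) and "The mITT population will include all subjects who receive a randomized study procedure" (SAP 5.2), where the SAP adds a post-blanking visit with efficacy data.
- PP: "The PP population will include all study subjects who receive their randomized procedure" (Protocol 9.3.3) and "The PP population will include all subjects who receive a randomized study procedure" (SAP 5.3), with visit and deviation conditions added.

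SAP 5 does name the wider group: "Randomized subjects will include all subjects randomized to a treatment arm". No efficacy analysis uses it.

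The trial is open-label (SAP 3.1), and subjects are randomized before the intra-op check (Protocol 4.6 and 5.1; SAP 3.1). Left atrial thrombus excludes in both arms. Adhesions exclude in the convergent arm only (Protocol 5.1). Excluded subjects have no study procedure, are replaced (Protocol 4.6; SAP 3.2) and are followed for 30 days. They are counted in disposition (SAP 8.1) and otherwise listed (SAP 3.2 and 13).

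On imputation, Protocol 9.3.1 continues: "Subjects randomized but with no post-treatment assessments will be imputed (refer to Section 9.4". Protocol 9.4 likewise imputes failure for randomized subjects without post-treatment data. SAP 7.2 limits this to subjects who were randomized and also received the procedure. SAP 13 returns to the wider wording, points to 7.2, and declares only the dropping of the six-month time point as a departure.

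**The concern.** An intention-to-treat comparison takes its protection from keeping everyone who was randomized in the assigned arm. Here entry depends on a step after an open-label assignment, and one criterion for failing that step exists in one arm only. If subjects excluded for adhesions would have done worse than average, their removal raises the convergent success rate while the control arm keeps its equivalents. The same gap covers anyone randomized and untreated for another reason, such as withdrawal after learning the allocation. This is the primary superiority test of a pivotal trial meant to support a premarket application, and no planned analysis would show how much depends on the missing subjects. The imputation texts also let two programmers defend different handling of a randomized, untreated subject.

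**Working it through.** **Coverage of each planned efficacy analysis**

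| Analysis | Set used | Includes randomized, untreated subjects? |
|---|---|---|
| Primary (SAP 9.1) | ITT | No |
| Population sensitivity (9.3.1) | mITT, PP | No |
| Tipping point (9.3.2) | mITT, ITT | No |
| Geography (9.3.3) | ITT | No |
| Multiple imputation (9.3.4) | ITT only | No |
| Secondary (9.2, 9.4) | ITT; mITT and PP optional | No |

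**Inputs.** From SAP 4 and 9.1: control success 40%, convergent 65%, two-sided alpha 0.05, power 80%, allocation 2:1, 10% dropout, 102:51. Assumed, because the documents give no value: the share f excluded from the convergent arm, and the success rate s those subjects would have had.

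**The plan's own figure.** Pooled-variance formula without continuity correction, mean rate (0.40 + 2×0.65)/3 = 0.567:

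n(control) = [1.960×√(1.5×0.567×0.433) + 0.842×√(0.40×0.60 + 0.65×0.35/2)]² / 0.25² = 45.7, so 46 control and 92 convergent, 138 in all. Per-arm inflation gives 46×1.1 = 50.6, so 51 control and 102 convergent: 153. Dividing 138 by 0.9 instead gives 154. The sample size is not in question.

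**Effect of the exclusion on the treated-only test.** Let success be 40% in both arms among all randomized. The treated convergent rate is then (0.40 − f×s)/(1 − f). Because excluded subjects are replaced, 102:51 are treated. A win is Pearson chi-square p<0.05 with higher convergent success. Exact binomial enumeration gives:

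| f | s = 0% | s = 20% | s = 40% |
|---|---|---|---|
| 0% | 2.5% | 2.5% | 2.5% |
| 1% | 2.8% | 2.7% | 2.5% |
| 2% | 3.1% | 2.8% | 2.5% |
| 5% | 4.4% | 3.3% | 2.5% |
| 10% | 7.4% | 4.5% | 2.5% |

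For example, at f = 5% and s = 0 the treated convergent rate is 0.40/0.95 = 42.1%, a bias of 2.1 points.

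**What counting them would do.** Suppose 2, 5 or 10 dropped convergent subjects truly fail, so the treated rate is 0.40×(102 + k)/102. The treated-only false-win rate is 3.1, 4.2 or 6.6%. With those subjects counted as failures it is 2.5, 2.4 or 2.3%.

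**What it would cost as the primary test.** Same enumeration, k convergent failures added to 102:51 treated:

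| k | Power, 65% v 40% treated | False-win rate, 40% v 40% treated (equal prognosis) |
|---|---|---|
| 0 | 84.0% | 2.5% |
| 2 | 79.9% | 2.0% |
| 5 | 76.1% | 1.4% |
| 10 | 63.9% | 0.8% |

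**When it could change a conclusion.** Control is 20/51 throughout.

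- 58/102 is the smallest convergent count that is significant (p=0.040; 57/102 gives 0.052). With two untreated convergent subjects added, p is 0.053 if neither succeeds, 0.040 if one does and 0.031 if both do.
- 66/102, about the design effect, gives p=0.003. With 2, 5 or 10 failures added, p is 0.004, 0.008 or 0.019.

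**The case against.** The case for leaving the plan alone has four parts.

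1. **The harm is assumed.** The documents give no exclusion rate and no link between adhesions and rhythm prognosis. Previous cardiac surgery and a history of pericarditis are already excluded (Protocol 4.3), so adhesions may be rare. At 1–2% exclusion with worse prognosis, the false-win rate is only 2.7–3.1%. This stands, and it limits the size of the point.
2. **Failure imputation is itself one-sided.** It penalizes the arm with the extra exclusion. No 12-month outcome exists for these subjects, since follow-up stops at 30 days and Protocol 5.1 foresees other AF treatment afterwards. This stands against requiring the imputed analysis as primary. It does not stand against reporting it.
3. **The restriction is open.** Protocol and SAP state the same definition, replacement is stated, and exclusions are counted. This is true, and it answers any suggestion of concealment. But counts in a disposition table are not a pre-specified analysis.
4. **SAP 7.2 may only make explicit the limit already in the first sentence of Protocol 9.3.1.** That reading is fair. It leaves SAP 13 restating the wider wording without declaring the narrowing.

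A reader might infer that the primary result is biased towards the device. The documents do not support that: they give neither the number excluded nor their prognosis, and equal prognosis means no bias. A reader might also infer that treated subjects with an incomplete lesion set drop out. They do not; the gap concerns only randomized, untreated subjects. Subjects given the other arm's procedure appear to stay in too, since SAP 5.1 accepts either procedure and analyses by randomized arm.

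**Conclusion.** The point holds in a limited form and should be fixed. The ITT label is wrong as written, no planned efficacy analysis covers all randomized subjects, and one post-randomization exclusion is specific to the convergent arm.

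The possible inflation is small if exclusions are rare: 2.8–3.1% against 2.5% at 2% convergent-only exclusion. It grows to 3.3–4.4% at 5% and 4.5–7.4% at 10%, for 20% down to 0% success among those dropped. These figures rest on assumed exclusion rates, a 40% null success rate among all randomized, and 102:51 treated after replacement. Only a borderline result would turn on a few subjects.

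The stronger conclusion, that the all-randomized set must become the primary one, does not follow. The missing outcomes would have to be imputed, and the power loss could be material. That choice belongs to the sponsor.

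**What to change.** 1. Rename the set in Protocol 9.3.1 and SAP 5.1 as a treated population, a form of modified ITT, under a name distinct from the existing mITT.
2. Define an all-randomized set by assigned arm, including replaced subjects. SAP 5 already describes this group.
3. Pre-specify the primary comparison on that set with untreated subjects counted as failures. Add a tipping-point analysis over their unknown outcomes in both arms, extending SAP 9.3.2. At the least, report both as sensitivity analyses beside the primary result.
4. Make Protocol 9.4, SAP 7.2 and SAP 13 agree on whether imputation applies to all randomized subjects or only to those who received a procedure, bring the imputation sentence of Protocol 9.3.1 into line, and declare any narrowing in SAP 13.

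As a sensitivity analysis this costs wording and a little analysis work, with no new data collection and no loss of power for the primary test. If the sponsor makes the failure-imputed set primary, the power and conservatism figures in the working show the price.

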5.2 Modified Intent-to-Treat (mITT) Population

The mITT population will include all subjects who receive a randomized study procedure (either EPi-Sense-AF or catheter ablation) and have at least one post-procedure follow-up visit after the 3 month blanking period (as described in Section 7.4.2) with non-missing efficacy results. This follow-up visit is defined as a visit with echocardiogram, rhythm disturbance evaluation, or Holter monitor results, after the end of the blanking period. This population will be used to support efficacy analyses. Subjects will be analyzed according to randomized treatment.

5.3 Per Protocol (PP) Population

The PP population will include all subjects who receive a randomized study procedure (either EPi-Sense-AF or catheter ablation) who have at least four of the five first year visits (that is, at least 4 of the 7 day, 1 month, 3 months, 6 months, and 12 months visits are completed) and who have no major protocol violations or deviations. This population will be used for sensitivity analysis of the primary efficacy analysis.

A blinded list of all protocol deviations will be provided to the Medical Monitor to be categorized (major or minor) prior to study unblinding and database lock, as described in Section 8.3.

Subjects will be analyzed according to randomized treatment.

5.4 Safety Population

The Safety population will include all subjects who receive a randomized study

procedure (either EPi-Sense-AF or catheter ablation). Subjects will be analyzed according to procedure received, in the event it differs from the randomized procedure. This population will be used for all safety analyses.

6 **CONSIDERATIONS FOR DATA ANALYSIS**

6.1 **Programming Environment**

All analyses will be conducted using SAS® version 9.3 or higher.

6.2 **Strata and Covariates**

There are no planned stratified analyses or adjustments for covariates, other than the subgroup analyses specified in Section 6.3 and potential adjustments for geographical location discussed in Section 9.3.3. Additional subgroup analysis and covariate adjustments will be performed as necessary.

6.3 **Subgroups**

A subgroup analysis of the primary endpoint will be conducted for the subgroup variables of:

- Geographic location - Europe, Region of United States (such as West, Southeast, Northeast, Central/Midwest) as per SAP section 9.3.3.
- Gender (M vs F).
- Age at baseline visit (<65 vs \geq 65 years).
- Body mass index (BMI; <30 vs \geq 30 kg/m²) at baseline visit,
- Access type (transdiaphragmatic or sub-xiphoid, which will be collected from source documentation, entered in a spreadsheet, finalized prior to database lock, and incorporated into analysis datasets).
- Left atrium size (< median value vs \geq median value, as recorded on the Pre-Procedure echocardiogram, based on the median of the ITT population). Other clinically relevant cut-points may be defined prior to unblinding the study.
- Left atrial volume (<median value vs \geq median value, as recorded on the CT Scan or MRI at the Baseline visit, based on the median of the ITT population). Other clinically relevant cut-points may be defined prior to unblinding the study.
- AF classification (Persistent versus Long-standing persistent AF).

For each of these, a logistic regression model will be fit to the primary endpoint, modeling for (1) treatment arm, (2) subgroup variable (dichotomous), and (3) interaction term of treatment arm * subgroup variable. A two-tailed alpha level of 0.15 will be used for determining poolablity of results. If the p-value of the interaction

term and subgroup variable are both >0.15 , the subgroup variable will be considered to not have significant impact and the subgroups will be pooled. If either is $p \leq 0.15$, the primary analysis will be presented for each level of that subgroup.

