#### **5.2 Study Procedure – Convergent Procedure Arm**

Once the procedure intra-op exclusion conditions have been evaluated, the epicardial lesion pattern will be created using the EPi-Sense-AF Guided Coagulation System with VisiTrax. The recommended study procedure outlined in Attachment A, and the Investigator's Training Guide should be followed to create the epicardial / endocardial lesion pattern.

Epicardial linear lesions will be created endoscopically using the EPi-Sense-AF Guided Coagulation System with VisiTrax throughout the posterior left atrium and along the pericardial reflections from a trans-diaphragmatic or sub-xiphoid access without any chest incisions. The

pericardial reflections will not be dissected. An endocardial ablation catheter will be used to ablate endocardially to connect lesions at the reflections to complete the isolation of the pulmonary veins, and create a cavotricuspid lesion to prevent typical atrial flutter. For patients with inducible atrial arrhythmias (atypical atrial flutter, atrial tachycardia, AVNRT, etc.) the arrhythmia may be mapped and ablated. If the subject does not organize into AT or SR, then the patient should be cardioverted through the administration of Ibutilide or electrical cardioversion. Posterior and other linear lesions such as a roof lesion and mitral valve isthmus lesion will not be created during the endocardial component of the convergent procedure.

Once the study lesion pattern has been created by coagulating cardiac tissue using the EPi-Sense-AF Guided Coagulation System and the endocardial ablation catheter, the pulmonary veins must be evaluated for entrance and/or exit block to confirm isolation. Follow the protocol provided in Attachment C to confirm pulmonary vein isolation.

The following procedure and post procedure data will be entered into the electronic data capture system developed for the study.

- TEE - Presence /absence of thrombi in LA
- Physicians performing the procedure
- Total Convergent procedure time  
*(Abdominal incision to removal of catheters-not sheath pull)*
- Total epicardial procedure time  
*(Abdominal incision to abdominal access site closure)*
- Total time to create the epicardial component of the lesion pattern  
*(Total epicardial ablation procedure time = time from first lesion to last lesion)*
- Epicardial system generator power setting
- Number of RF applications for EPi-Sense-AF Guided Coagulation system
- Max Power setting for the endocardial lesions

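### Access type exists only in the convergent arm, so the arm-by-access interaction planned in SAP 6.3 cannot be estimated and its pooling rule cannot be applied as written

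*SAP*

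**What the plan says.** SAP 6.3 (Subgroups) names eight variables for a subgroup analysis of the primary endpoint: geographic location, gender, age, BMI, access type, left atrial size, left atrial volume and AF classification. The access-type entry reads "Access type (transdiaphragmatic or sub-xiphoid, which will be collected from source documentation". It is to be finalised before database lock.

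One model serves all eight, "modeling for (1) treatment arm, (2) subgroup variable (dichotomous), and (3) interaction term of treatment arm * subgroup variable". The decision rule follows: "A two-tailed alpha level of 0.15 will be used for determining poolablity of results". If the interaction and subgroup p-values are both above 0.15, "the subgroup variable will be considered to not have significant impact and the subgroups will be pooled". If either is at or below 0.15, "the primary analysis will be presented for each level of that subgroup". Section 6.3 makes no exception for access type and does not say how controls are to be coded.

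Protocol 5.2 describes the two routes for the convergent arm, where epicardial lesions are made "throughout the posterior left atrium and along the pericardial reflections from a trans-diaphragmatic or sub-xiphoid access without any chest incisions". Attachment A has a subsection on each route. Protocol 5.3 and Attachment B give the control arm an endocardial catheter procedure through venous and transseptal access, with no epicardial step.

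Protocol 9.8 has the same model but lists only gender, age, BMI, and left atrial size and volume. All of these exist in both arms. Access type was added in the SAP.

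**The concern.** An interaction asks whether the treatment effect differs between levels of a variable. That needs treated and control subjects at each level. Here the variable describes how one of the two procedures was performed, so the control half of the comparison does not exist.

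Three planned steps are affected: the interaction p-value, the decision to pool, and the presentation by level if pooling is refused. If the entry stays, someone must decide how to code controls when the model fails, possibly after results are known, in an open-label trial meant to support a premarket application. The likely visible result is an undefined or improvised access-type row in the planned subgroup forest plot (Figure 14.2.1.5).

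**Working it through.** **Inputs.** Arm sizes 102 and 51, success rates 65% and 40%, two-sided alpha 0.05, 80% power, 2:1 allocation and 10% dropout (SAP 4); pooling level 0.15, two-tailed (SAP 6.3). The documents do not give the split between access routes. I assume 51/51 for the design matrix; its rank is the same for any split in which both routes occur.

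**Step 1: the plan's own figure.** With pooled variance and no continuity correction, the pooled rate is (0.40 + 2 × 0.65)/3 = 0.567. Controls needed:

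[1.96 × √(1.5 × 0.567 × 0.433) + 0.842 × √(0.40 × 0.60 + 0.65 × 0.35/2)]² / 0.25² = 45.7, so 46, and 3 × 46 = 138 in total.

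Dropout gives 138/0.9 = 153.3 (154 rounded up) or 138 × 1.1 = 151.8 (152 rounded up). The stated 153 is reproduced within rounding. Access type plays no part in it.

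**Step 2: what the interaction needs.** Let T = 1 for convergent and A = 1 for one of the two routes:

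logit(p) = b0 + b1·T + b2·A + b3·T·A

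b3 = (convergent log-odds at A = 1 minus at A = 0) − (control log-odds at A = 1 minus at A = 0).

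The second bracket needs controls at both levels. By the protocol's description of the procedures there are none at either.

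**Step 3: rank under each coding of controls.**

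| Coding of controls | Dependency between columns | Rank |
|---|---|---|
| All set to A = 0 | T·A equals A | 3 of 4 |
| All set to A = 1 | A equals 1 − T + T·A | 3 of 4 |
| Missing, so dropped | T equals the intercept, T·A equals A | 2 of 4 |
| Third level for no access | T equals the sum of the two route indicators; each interaction column equals its indicator | 3 of 6 |

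A numerical rank check gave the same results. In no row is b3 identified. In the third row the arm effect is lost too. The fourth row also breaks the SAP's requirement of a dichotomous variable.

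**Step 4: the decision rule.** The pooling branch needs an interaction p-value, and there is none. The other branch can still be triggered: if software drops the redundant column, it may report an access p-value, which is the contrast of the two routes within the convergent arm. Even with no true difference between routes, a test at 0.15 crosses its threshold about 15% of the time. The rule would then call for a between-arm analysis at each access level, where no controls exist.

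**Step 5: what the data can show.** Only the contrast within the convergent arm is estimable. Assuming about 65% success and all 102 subjects, the difference detectable with 80% power at two-sided 0.15 is (1.440 + 0.842) × √[0.65 × 0.35 × (1/n1 + 1/n2)]:

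| Split of 102 | Detectable difference |
|---|---|
| 51/51 | 22 points |
| 30/72 | 24 points |
| 20/82 | 27 points |
| 10/92 | 36 points |

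A non-significant access p-value would therefore be weak evidence that the routes perform alike, apart from saying nothing about the treatment effect.

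**The case against.** **The route may be a site habit.** Randomisation is blocked by site. If each site used one route, controls could be given their site's route and an interaction could be fitted. The documents do not rule out such a practice. But the SAP defines no site-level variable, and taking access type from source documentation reads more naturally as the route used in that subject. A site-assigned route would be a different variable needing its own definition.

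**Crossovers could fill the empty cells.** A control who received the convergent procedure would have an access type, and SAP 5.1 analyses that subject as randomised. A few such subjects would not support a usable interaction.

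**The convergent-arm restriction is obvious.** SAP 8.7 does recognise that procedure data differ by arm and presents them separately. Section 6.3 has no such provision. SAP 6.2 allows additional subgroup analyses as necessary, which would permit a within-arm summary but does not repair the stated rule.

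**The consequence is small.** This stands. The primary analysis is an unadjusted two-arm chi-square test, and subgroup tests lie outside the fixed sequence of 19 in SAP 9.2. A programmer would probably meet the problem on the first run.

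**Stronger readings.** A reader might infer that the whole subgroup analysis fails. It does not: the other seven variables exist in both arms. A reader might also infer that the route is chosen after randomisation. No passage says when, by whom or on what basis it is chosen. The non-randomised label does not depend on timing: an attribute recorded in one arm only defines no matching set of controls. Finally, it would go too far to say that the 0.15 rule returns nothing for access type, since an access p-value may print and trigger presentation by level.

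**Conclusion.** The point holds for one of eight subgroup models. With access type taken as the route used in the subject, two of the four arm-by-access cells are empty or undefined. The interaction has no estimate under any coding of controls examined, the pooling rule cannot be applied as written, and the primary comparison cannot be presented by access level. This is a stated rule that cannot be executed, rather than a missing detail.

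The finding is structural. It rests on the protocol's description of the two procedures, not on any success rate, sample size or split of routes. The detectable differences in the working do rest on assumptions (65% success, 102 subjects, the splits shown), but they serve only to describe the within-arm contrast. The primary test, the sample size and the study's main conclusion are unaffected. It should be corrected before database lock, but it does not threaten the trial.

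**What to change.** In SAP 6.3, remove access type from the variables subject to the interaction model and the 0.15 pooling rule. In its place, prespecify the primary-endpoint success rate with confidence intervals by access type within the convergent arm only, as a descriptive summary. If either access group is also set against all controls, label that comparison non-randomised. Adjust the access-type row of Figure 14.2.1.5 to match.

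A breakdown of major adverse event rates by access type is optional; SAP 6.3 covers only the primary efficacy endpoint.

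SAP 9.3.4 also lists access type as a candidate covariate for the multiple-imputation model, which covers both arms. It is undefined for controls there as well. Either drop it from that list or state how controls are handled.

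The cost is one SAP bullet and one check of the imputation list. No new data are needed, since access type is already to be collected and finalised before database lock.
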